### 6.4.3. Laboratory-Confirmed SARS-CoV-2 Infection Obtained Outside of the Study

If a site receives notification from a participant that a positive test result for SARS-CoV-2 infection was obtained outside of the study, the test result will be obtained and documented, and the participant will have an unscheduled study visit as soon as feasible. If the outside documented positive test utilized any assay type other than RT-PCR, the participant will have samples collected to perform local RT-PCR and central RT-qPCR testing for SARS-CoV-2 infection. If the outside test utilized RT-PCR, the participant will only require sample collection for central RT-qPCR testing. In all cases, participants will undergo an evaluation of COVID-19 signs and symptoms by the investigator or designee during the unscheduled visit.

Test results outside of the study will qualify as laboratory-confirmed SARS-CoV-2 infection for the purposes of study analyses, but only if an RT-PCR assay was utilized.

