#### **6.4.4. Post-Infection Treatment for Participants with Confirmed Positive SARS-CoV-2 RT-PCR**

Participants with a confirmed positive SARS-CoV-2 RT-PCR at any time during the study (local, central, or documented outside of the study) should be treated with standard of care per local practices and per the investigator's judgment. In addition, casirivimab+imdevimab may be offered to the participant as post-infection treatment if medically appropriate in the investigator's judgment.

If post-infection treatment with casirivimab+imdevimab is deemed medically appropriate, the treatment should be provided through the most expeditious mechanism available. To this end, casirivimab+imdevimab may be given through mechanisms outside of the study in regions where it is approved or authorized. Where regionally approved or authorized, casirivimab+imdevimab should be administered at the approved or authorized dose.

For participants who are able to receive post-infection care at a study site, casirivimab+imdevimab may also be offered to the participant as part of the study. This mechanism can be used, for example, if casirivimab+imdevimab is not regionally approved or authorized for treatment of SARS-CoV-2 infection, or if treatment cannot be made available in an expeditious manner via the approved or authorized mechanisms.

The following investigational dose levels will be offered as part of the study, and may be provided if medically indicated in the investigator's judgement:

- Not hospitalized due to COVID-19 and does not require supplemental oxygen or an increase in baseline oxygen flow rate due to COVID-19: **1200 mg** (600 mg per mAb), administered either intravenously or subcutaneously
- Hospitalized due to COVID-19 and does not require supplemental oxygen due to COVID-19, or requires low-flow supplemental oxygen due to COVID-19: **2400 mg** (1200 mg per mAb), administered intravenously
- Hospitalized due to COVID-19 and requires either high-intensity supplemental oxygen due to COVID-19 or requires mechanical ventilation due to COVID-19: **8000 mg** (4000 mg per mAb), administered intravenously

If feasible, treatment with casirivimab+imdevimab should be provided within 48 hours after a positive RT-PCR result is obtained.

Administration of post-infection treatment with casirivimab+imdevimab will not require unblinding of the participant's randomization assignment (Section 8.7).

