4.5. Efficacy Variable

4.5.1. Primary Efficacy Variable

Primary efficacy variable is cumulative incidence of symptomatic (broad term), RT-PCR-confirmed SARS-CoV-2 infection cases during the efficacy assessment period (EAP). The conditions for symptomatic SARS-CoV-2 infection are as follows:

- At least 1 sign or symptom (broad term definition) confirmed by a study clinician (investigator or designee) to be related to COVID-19, **and**
- A positive SARS-CoV-2 RT-PCR result (local or central analysis), **with**
- The sign/symptom onset date and the date of collection for the positive sample occurring within ± 7 days of one another

The primary endpoint will analyze symptomatic SARS-CoV-2 infection during the efficacy assessment period (EAP). The EAP is defined as the day 2 to day 169 +7 days . In addition, following rules will be applied to the primary analyses:

- Time to first symptomatic infection is defined as the first date of having either central or local lab determined positive test result.
- Subjects do not experience any symptomatic infection will be censored at last observed time point.
- Subjects who die at any time in the study or discontinue the study earlier (did not get any infections) will be censored at the end of study in case of final database lock.
- Subjects with COVID-19 symptoms that are missing a central lab determined RT-qPCR test during the EAP but have a positive SARS-CoV-2 test from a local lab will be considered as having a symptomatic infection if any of the symptoms occurred within 7 days of the positive SARS-CoV-2 test that was observed during the EAP.
- If subjects took optional dose of 1200mg, all the data after the dose will be removed from the efficacy analyses.

If subjects took investigational, authorized, or approved COVID-19 vaccines within 90 days of the last dose of study drug (or per current CDC recommendations) (CDC, 2021) or any covid-19 treatment medications for prevention after starting study treatment (Anti SARS-CoV-2 antibodies including Bamlanivimab/ Etesevimab, Casirivimab/ Imdevimab (REGEN-COV), Sotrovimab or Tixagevimab/ Cilgavimab (Evusheld); remdesivir; Nirmatrelvir/ Ritonavir (Paxlovid); Molnupiravir, all the efficacy data after these treatment will be removed from efficacy analyses.

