5.7.1. Analysis of Primary Efficacy Endpoint

The mITT population will be the primary analysis population for efficacy. The ITT population will also be used for primary efficacy analysis. Participant data will be analyzed according to the group to which they were randomized.

The primary endpoint of the study is cumulative incidence of symptomatic (broad term), RT-PCR-confirmed SARS-CoV-2 infection cases during the efficacy assessment period (EAP). See Section 4.5.1 for the definition of a symptomatic SARS-CoV-2 infection.

The cumulative incidence of cases through the EAP will be estimated using the Kaplan-Meier method, and the antibody efficacy (AbE) will be estimated as the percent risk reduction (ie, $100 \times [1-HR]$, where HR is the hazard ratio for comparison of the incidence of cases in the antibody arm versus placebo). A unstratified Cox proportional hazard regression model with treatment group as a fixed effect, will be used to estimate the hazard ratio and 95% CI (2-sided). Nominal two-sided p-values will be reported for descriptive purpose using the log-rank test for pairwise comparison between each antibody arm and placebo.

For the primary analysis, cases will be counted from day 2 through day 176 (ie, day 169 +7 days), to allow for cases to accrue until the end of the EAP visit window per the Schedule of Events. Time of symptomatic SARS-CoV-2 infection will be the earlier of the sign/symptom onset date or the sample collection date for which RT-PCR result (local or central) was positive.

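### Protocol 6.4.3 counts outside RT-PCR positives in study analyses, but the case and event-date rules in the protocol and SAP name only local or central results

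*SAP*

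**What the plan says.** **Rules that count outside results.** Protocol 6.4.3: "Test results outside of the study will qualify as laboratory-confirmed SARS-CoV-2 infection for the purposes of study analyses", on condition that the assay was RT-PCR. It also sets what is sampled next: "If the outside test utilized RT-PCR, the participant will only require sample collection for central RT-qPCR testing". No study local RT-PCR follows in that situation. Protocol 6.4.4, on who has a confirmed positive, lists three sources: "local, central, or documented outside of the study".

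**Rules that define and date a case.** SAP 4.5.1 requires "A positive SARS-CoV-2 RT-PCR result (local or central analysis"), with symptom onset and sample collection no more than 7 days apart. It dates the event thus: "Time to first symptomatic infection is defined as the first date of having either central or local lab determined positive test result". SAP 5.7.1 takes the earlier of symptom onset and "the sample collection date for which RT-PCR result (local or central) was positive". SAP 1.1 repeats the case definition and the 5.7.1 date rule. Protocol 6.2 and 11.4.3.1 contain the same two-source wording.

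**Rule for a missing central test.** SAP 4.5.1 accepts symptomatic participants who are "missing a central lab determined RT-qPCR test during the EAP but have a positive SARS-CoV-2 test from a local lab", if a symptom fell within 7 days of that test. RT-PCR is not named for the local test in this rule.

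The SAP nowhere mentions tests obtained outside the study, and its list of departures from the protocol (1.2.4) covers only dropped exploratory endpoints.

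**The concern.** The plan gives two answers to the question of which positive results make a participant a case, and a programmer working from the SAP sees only one of them. After an outside RT-PCR the study takes only a central swab. If that swab is late, negative or not taken, the outside result is the only positive near onset. Under Amendment 2 all assessments of suspected COVID-19 are optional for site and participant (protocol 9.1.2, footnote 6), so an absent swab is a realistic outcome.

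At stake are the primary endpoint and the two exploratory endpoints that borrow its rules (SAP 4.5.2, items 1 and 2). Item 2, infection regardless of symptoms, is the most exposed: protocol 3.2.1.3 gives outside testing as the reason for having that endpoint. A participant could also be a confirmed positive under protocol 6.4.4 and be analysed as uninfected.

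**Working it through.** **Step 1: apply the rules to four constructed records.** All days fall within the counting window of day 2 to day 176. *Narrow* means that an outside test is neither local nor central. *Broad* means that an outside laboratory is treated as a local laboratory.

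| Record | SAP, narrow | SAP, broad | Protocol 6.4.3 |
|---|---|---|---|
| A. Onset day 38; outside RT-PCR positive day 40; central swab positive day 50 | Central sample is 50 − 38 = 12 days from onset, over 7: no case | Outside sample is 40 − 38 = 2 days from onset: case | Case |
| B. As A, but central swab negative or not taken | No case, and no infection for 4.5.2 item 2 | Case | Case |
| C. No symptoms; outside RT-PCR positive day 40; central swab positive day 50 | Infection dated day 50, which is 50 − 40 = 10 days late | Infection dated day 40 | Infection, positive from day 40 |
| D. Onset day 38; outside non-PCR positive day 40; no study RT-PCR taken | No case | Case through the missing-central rule | Not a case |

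The narrow reading fails on A, B and C. The broad reading fails on D. Neither agrees with protocol 6.4.3 throughout. For D, the general condition in SAP 4.5.1 does ask for RT-PCR, but the more specific missing-central rule omits it, so the section can be programmed either way.

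A symptomatic participant with a positive central swab within 7 days of onset is a case on every reading. Only the date can then move, and only under the 4.5.1 date rule, which ignores onset. Under the 5.7.1 rule the onset date still governs when it comes first.

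**Step 2: scale.** Inputs are the 6-month rates in protocol Table 6 (4.02%, 1.628%, 1.829% and 2.231%) and 66 participants in four arms (SAP 2.1: 16 to 17 per arm; 16.5 used here).

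- The antibody-arm rates reproduce from the placebo rate. The hazard is −ln(1 − 0.0402) = 0.04103. With HR 0.40, 0.45 and 0.55, 1 − exp(−HR × 0.04103) gives 1.628%, 1.829% and 2.231%.
- Expected symptomatic cases over a full 6 months: 16.5 × (4.02 + 1.628 + 1.829 + 2.231)% = 16.5 × 9.708% = 1.60.
- One case in an arm: 1/16 = 6.3% and 1/17 = 5.9%, so about 6 percentage points.
- Share of cases with only an outside positive near onset: not given. If it is assumed to be 5% to 30%, the expected loss on the narrow reading is 1.60 × 0.05 = 0.08 to 1.60 × 0.30 = 0.48 cases. This range illustrates scale and is not an estimate.

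**The case against.** The strongest reply is that the SAP does not depart from the protocol. Its case definition is that of protocol 6.2, and its date rule in 5.7.1 is that of protocol 11.4.3.1. This stands. A reader might infer that the SAP narrows the protocol's definition without declaring it; the documents do not support that. The inconsistency lies inside the protocol, and the SAP carries it forward without the 6.4.3 rule.

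The second reply is that local can be read to include outside RT-PCR. At screening a historical negative is accepted under a local-assay criterion (protocol 7.2.1, criterion 5), and Table 1 labels that test local. In 6.4.3 an outside RT-PCR removes the need for a local one, as if it filled that slot. This reading is reasonable, and it means that loss of cases is not established. It does not settle the matter: protocol 6.4.4 lists outside results separately, and the broad reading produces record D.

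The third reply is that the consequence is small. SAP section 1 says that the hypotheses are not evaluable, the analyses are descriptive and the p-values nominal. SAP 4.5.1 removes efficacy data after the optional dose, so later outside tests in those participants are irrelevant. Record A needs a 10-day gap before the central swab, although 6.4.3 asks for a visit as soon as feasible. All of this stands and limits the weight of the point.

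**Conclusion.** The conflict is real: the stated rules give different case lists, and neither reading of local brings the SAP into line with protocol 6.4.3. It deserves correction because the change is small and decides who counts as a case. Its reach is limited to a descriptive analysis of 66 participants.

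The number of affected participants cannot be obtained from the documents. The 1.60 expected cases rest on the planning rates and a full 6 months of follow-up for everyone, which early closure and the data-removal rules make generous. With so few cases, one dropped or wrongly admitted moves an arm's crude incidence by about 6 percentage points.

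Three stronger inferences are not supported. Nothing shows that outside testing became a main source of confirmation after Amendment 2; the documents say only that study testing became optional. No percentage understatement of incidence can be given, because it would only restate the assumed share. Nothing indicates that the arms would be affected differently in this blinded comparison.

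**What to change.** 1. In SAP 4.5.1 and 5.7.1, define the accepted result as a positive RT-PCR that is local, central, or documented outside the study under protocol 6.4.3. SAP 4.5.2 items 1 and 2 inherit this by reference; the summary in SAP 1.1 should match.
2. Use the outside RT-PCR sample date for the 7-day rule, and as one candidate sample date in the existing rule that takes the earlier of symptom onset and positive sample collection. It should not replace that rule: in record A the event date is onset, day 38, not day 40. Word the date sentence in SAP 4.5.1 to agree with 5.7.1.
3. Restrict the missing-central rule in SAP 4.5.1 to RT-PCR, so that outside non-PCR positives stay excluded.
4. Reconcile protocol 6.2 and 11.4.3.1 with 6.4.3.
5. Confirm that outside RT-PCR results and sample dates are in the analysis data. Protocol 6.4.3 requires the result to be obtained and documented, but the recording lists in 9.2.4.2 and the Amendment 2 procedures name only local and central results.

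The cost is a few sentences in the SAP, a protocol clarification and a data check in at most 66 participants. If outside results were kept only in source records, sites would have to be queried. No new study procedure is needed.

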### **6.6. End of Study Definition**

The end of study is defined as the date the last participant completes the last study visit, withdraws from the study, or is lost to follow-up (ie, the participant can no longer be contacted by the study site).

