Post-Infection Treatment. Participants with confirmed positive SARS-CoV-2 RT-PCR will be eligible for post-infection treatment (as described in protocol Section 6.4.4) at any time prior to receipt of the optional 1200mg SC dose (eg, during the 4 weeks between receipt of the last protocol-defined dose and optional 1200 mg SC dose). Once this optional dose has been

administered, post-infection treatment will no longer be offered. Likewise, any participant who receives post-infection treatment will not be eligible to receive the optional 1200 mg SC dose.

Participants with Positive SARS-COV-2 RT-PCR. Participants with a positive SARS-CoV-2 RT-PCR may have additional assessments and sample collections, including unscheduled visits every 7

days (± 1 day) for central laboratory RT-qPCR analysis until 2 consecutive negative test results are obtained:

- NP swab samples for RT-qPCR
- COVID-19 signs and symptoms evaluated by the investigator or designee
- Information regarding COVID-19-related medically-attended visits (MAVs; defined in protocol Section 9.2.4.3)

End-of-Study Visit

All participants, including those who do not consent to receive the optional final dose, will have a follow-up (end-of-study) telephone visit approximately 85 days (3 months) from their last dose of investigational drug (casirivimab+imdevimab or placebo) to monitor safety. Study assessments for the 3-month follow-up visit will be limited to the collection of targeted adverse events, as detailed in the new schedule of events (protocol amendment 2 Table 2).

Sites will ensure that an additional discussion about the potential risks and benefits to the participant and fetus is discussed as part of re-consent for participants who become pregnant during the study.

Analysis Plan

At the time that enrollment was closed, 66 participants had been enrolled in the study. Due to the early study closure and the resulting small sample size of enrolled participants, all analyses will be performed descriptively and only numeric comparisons will be performed. All safety endpoints (including AEs, TEAEs, AESIs, SAEs, and safety laboratory values) will be summarized. Selected efficacy, virology, PK, and/or immunogenicity data may also be analyzed descriptively. No interim analysis will be performed for this study, and no IDMC review meetings will occur.

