6.4. Visit Windows

Assessments taken outside of protocol allowable windows will be displayed according to the case report form (CRF) assessment recorded by the investigator. Data analyzed by-visit-analysis will be summarized by the scheduled visit described in protocol Schedule of Events. Below are the definitions for the visit windows programmatically imposed on all available measures from unscheduled visits collected over the course of the study including early termination visit and end of study visit. No analysis visit windows will be applied for the study scheduled visits nor for drug concentration and immunogenicity data. The visit windows are constructed using ranges

applied to the number of days in study (study days) when the measure is collected. Below are the relevant definitions for the analysis visit windows:

1. The first study treatment occurs on Study Day 1.
2. Study day is defined as the number of days since the first study treatment administration+1.
3. Since the protocol specifies that measurements be collected before study treatment is administered on a given day, it is appropriate that baseline include Day 1.
4. For randomized but not treated subjects, Day 1 is the day of randomization.

Table 1: Efficacy Analysis Windows for Unscheduled Visits with RT-qPCR or Viral Load Results

Visit Label	Targeted Study Day	Window in Study Day
Baseline	1	≤ 1
Week 1	8	[2, 11]
Week 4	29	[22, 36]
Week 8	57	[50, 64]
Week 12	85	[78, 92]
Week 16	113	[106,120]
Week 20	141	[134, 148]
Week 24	169	[162,176]
Week 28	197	[183, 211)
Week 32	225	[211, 239)
Week 36	253	[239, 267]

If a subject has multiple efficacy assessment visits within an analysis visit window, the one with worst result (e.g., the positive test result will be used for analysis if one record is positive and the

other one is negative; the highest viral load result will be used if multiple viral load results are in the same analysis window.) will be selected. If the test results are all negative, the value of the latter visit will be used. If there are multiple positive RT-qPCR results within an analysis window, the record with the highest quantitative result will be used.

Table 2: Global Analysis Windows for Data Other Than RT-qPCR Test

Visit Label	Targeted Study Day	Window in Study Day
Baseline	1	≤ 1
Week 1	8	[5, 11]
Week 4	29	[22, 36]
Week 8	57	[50, 64]
Week 12	85	[78, 92]
Week 16	113	[106,120]
Week 20	141	[134, 148]
Week 24	169	[162,176]
Week 28	197	[183, 211)
Week 32	225	[211, 239)

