6.6. Statistical Technical Issues

7. INTERIM ANALYSIS

This study is terminated early and there's no planned interim analysis.

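### SAP 4.5.1 censors uninfected participants who die or leave early at an undefined end-of-study date, which can fall after they were last observed

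*SAP*

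**What the plan says.** SAP 4.5.1 lists rules for the primary time-to-event variable. The general one is: "Subjects do not experience any symptomatic infection will be censored at last observed time point". The next bullet reads, for uninfected participants who die or leave early: "discontinue the study earlier (did not get any infections) will be censored at the end of study in case of final database lock". The section also cuts follow-up short in two situations. After the optional 1200 mg dose, "all the data after the dose will be removed from the efficacy analyses". Efficacy data are likewise removed after a COVID-19 vaccine or "any covid-19 treatment medications for prevention after starting study treatment".

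The SAP does not define end of study. The documents use the term in several ways:

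- Protocol 6.6, the only formal definition, is at trial level: "The end of study is defined as the date the last participant completes the last study visit", withdraws or is lost to follow-up.
- SAP 1.1 uses it for a participant's closing call: all participants "will have a follow-up (end-of-study) telephone visit approximately 85 days (3 months) from their last dose of investigational drug".
- SAP 6.4 mentions it among a participant's visits: "including early termination visit and end of study visit".
- SAP 10.1, Table 3, labels the day 253 visit EOS.

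SAP 5.7.1 counts cases from day 2 through day 176 and specifies Kaplan-Meier incidence, an unstratified Cox hazard ratio with 95% CI, and nominal log-rank p-values. It gives no censoring rule. SAP 6.2 points to 5.7 for missing RT-qPCR results only, and SAP 6.3 is silent on efficacy censoring. SAP 4.5.2 applies similar rules to two further time-to-event variables.

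**The concern.** An uninfected participant who dies or withdraws meets both bullets. Two programmers working from this text could derive different censoring dates and so different risk sets.

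The more serious part is the date itself. Censoring should end a person's time at risk when observation ends. If a leaver is instead carried to a later date, that person stays in the denominator as event-free although no case could have been recorded. Kaplan-Meier incidence is then too low. The relative comparison could also move if exits are unbalanced between arms.

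The qualifier about the final database lock does not help. It might have separated a final analysis from an interim one, but SAP 7 says: "This study is terminated early and there's no planned interim analysis". The final lock is the only one described.

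**Working it through.** **1. How far past exit each reading can reach.** Take a participant whose last dose was on day 29 and who leaves uninfected on day 30.

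| Reading of end of study | Censoring day | Unobserved days added |
|---|---|---|
| Own exit | 30 | 0 |
| Nominal closing call, last dose + 85 | 29 + 85 = 114 | 114 − 30 = 84 |
| Day 253 EOS, capped at day 176 | 176 | 176 − 30 = 146 |
| Protocol 6.6 trial-level date, capped at day 176 | up to 176 | up to 146 |

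The last row is a maximum. It needs the trial-level date to fall on or after that person's day 176, and the documents do not give that date.

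**2. Inputs.** Placebo incidence 4.02% over 6 months, 5% dropout by 6 months and 10% loss from ITT to mITT (Protocol 11.2); 2188 randomised per arm (Table 6). Event and dropout times are taken as exponential over 168 days; the plan states this for events, and for dropout it is an assumption.

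- Event hazard: λ = −ln(1 − 0.0402)/168 = 0.0002442 per day.
- Dropout hazard: μ = −ln(1 − 0.05)/168 = 0.0003053 per day.

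**3. Reproducing the plan's own figure.** The probability of an observed case before leaving is

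λ/(λ+μ) × [1 − exp(−(λ+μ) × 168)] = 0.4444 × 0.08819 = 3.919%.

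Placebo cases: 0.9 × 2188 × 3.919% = 1969.2 × 3.919% = 77.2, against 77 in Table 6. The inputs are therefore used as the plan uses them.

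**4. Effect on cumulative incidence.** Censoring at exit, with exits independent of infection risk, makes Kaplan-Meier estimate 1 − exp(−168λ) = 4.020%. If leavers are kept at risk through the period, Kaplan-Meier reduces to the proportion in step 3.

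| Dropout by 6 months | Censored at exit | Carried through | Relative change |
|---|---|---|---|
| 5% (plan) | 4.02% | 3.92% | −2.5% |
| 10% (assumed) | 4.02% | 3.82% | −5.1% |
| 20% (assumed) | 4.02% | 3.61% | −10.3% |

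At day 176 with 5% dropout: 4.10% instead of 4.21%.

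**5. Effect on the hazard ratio.** With leavers carried, each arm has case density f(t) = λ·exp(−(λ+μ)t) and at-risk fraction Y(t) = 1 − λ/(λ+μ) × [1 − exp(−(λ+μ)t)]. The large-sample Cox estimate θ solves ∫[f_a − (f_a + f_p)·θY_a/(θY_a + Y_p)]dt = 0 to day 176. For a true hazard ratio of 0.40:

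- dropout 5% in both arms, or 20% in both: 0.40;
- placebo 20%, active 5% (assumed): 0.44;
- placebo 5%, active 20% (assumed): 0.37.

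**6. Scale in this trial.** There are 66 participants, so 66/4 = 16.5 per arm.

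- Leavers at the planned rate: 66 × 0.05 = 3.3 in all, 0.8 per arm.
- Expected cases at Table 6 rates with full follow-up: 16.5 × (1.628% + 1.829% + 2.231% + 4.02%) = 16.5 × 9.708% = 1.60.
- Chance of no case in any arm: (0.98372 × 0.98171 × 0.97769 × 0.9598)^16.5 = 0.197.
- Chance of a case in both arm 1 and placebo: (1 − 0.98372^16.5) × (1 − 0.9598^16.5) = 0.237 × 0.492 = 0.117.
- With the planned 10% mITT loss, 14.85 per arm: 14.85 × 9.708% = 1.44 expected cases.
- An arm of 16 with one case after one leaver: 1/15 = 6.67% if censored at exit, 1/16 = 6.25% if carried.
- An arm with no case shows 0% under either rule.

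**The case against.** **The specific bullet governs.** The first bullet is general and the second addresses deaths and early leavers, so the usual convention lets the second prevail. That is a fair reading and weakens the complaint about precedence. It leaves the date undefined, however, and it selects the bullet that can extend time at risk.

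**A participant-level reading removes the problem.** A reader might infer that the bias arises only with the trial-level date. The documents do not support that. Their participant-level uses include the closing call and the day 253 visit, and an early leaver may be gone before either. Only the participant's own exit date is free of the problem, and the SAP does not say that this is meant.

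**The efficacy comparison is biased.** A reader might also infer this, or that every day-30 leaver gains 146 days. Neither follows. With equal dropout the hazard ratio is essentially unchanged; the 0.44 and 0.37 rest on a 20% versus 5% split that appears nowhere in the documents. The 146 days is an upper limit. Nor is it unclear whether deaths are censored: the bullet says they are, and only the date is open.

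**Nothing turns on it.** SAP 1 designates all endpoints exploratory and says no hypothesis is evaluable. SAP 1.1 makes all analyses descriptive, and SAP 5.7.4 drops multiplicity adjustment. Removing data after the optional dose further shortens the time affected. All of this stands and sets the weight of the point.

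**Conclusion.** The point holds and is minor. SAP 4.5.1 states a censoring date that, under the protocol's formal definition or either nominal visit date, can fall after the participant was last observed. That makes Kaplan-Meier incidence too low. The size is 0.10 percentage points at the planned placebo rate and dropout, assuming exponential times, exits unrelated to infection risk, and leavers carried through the whole period. Actual dropout is not given; the 10% and 20% rows show the range.

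In an arm of 16 or 17, one leaver can still change a reported percentage, but only if a case occurs later in that arm. With about 1.6 cases expected across four arms, and fewer in the mITT set or with shortened follow-up, a finite non-zero hazard ratio for arm 1 against placebo is itself unlikely. The effect is confined to descriptive estimates.

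**What to change.** Replace the two censoring bullets in SAP 4.5.1 with one rule: *participants without a qualifying event are censored at the earliest of death, study discontinuation, last observed time point, the optional 1200 mg dose or other data-removal point already specified in this section, and day 176.*

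Apply the same rule to the time-to-event variables in SAP 4.5.2. For the follow-up-period variable, use the participant's last study visit in place of day 176. With an earliest-of rule the SAP need not refer to end of study for censoring at all.

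The cost is one sentence and one derivation. Compared with carrying leavers forward, person-time is slightly shorter and intervals slightly wider.
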